### **Reliever Medication**

Reliever medications will be supplied by sites and reimbursed as per country regulation or by Sponsor's local affiliate as locally required.

Patients may administer albuterol/salbutamol or levalbuterol/levosalbutamol or ipratropium or ipratropium/short-acting  $\beta$  agonists [SABA] combinations or terbutaline as needed during the study. Nebulizer solutions may be used as an alternative delivery method.

Formulation: MDI, nebulizer solutions or DPI

Route of administration: oral inhalation

Dose regimen: as prescribed

Study personnel will convert salbutamol/albuterol nebulizer and levosalbutamol/levalbuterol nebulizer use as shown on the following tables:

**Table 3 - Reliever medication - Salbutamol/Albuterol nebulizer solution**

Salbutamol/Albuterol Nebulizer Solution -Total Daily Dose (mg)	Number of Puffs*
2.5	4
5.0	8
7.5	12
10	16

\*Conversion factor: salbutamol/albuterol nebulizer solution (2.5 mg) corresponds to 4 puffs

- Example of salbutamol/albuterol nebulizer-to-puff conversion: Patient received 3 salbutamol/albuterol nebulizer treatments (2.5 mg/treatment) between 7 and 11 AM. Total daily = 7.5 mg or 12 puffs.

**Table 4 - Reliever medication - Levosalbutamol/Levalbuterol nebulizer solution**

Levosalbutamol/Levalbuterol Nebulizer Solution -Total Daily Dose (mg)	Number of Puffs*
0.63	2
1.25	4
2.5	8
3.75	12
5	16

\*Conversion factor: levosalbutamol/levalbuterol nebulizer solution (1.25 mg) corresponds to 4 puffs

- Example of levosalbutamol/levalbuterol nebulizer-to-puff conversion: Patient received 3 levosalbutamol/levalbuterol nebulizer treatments (1.25 mg/treatment) between 7 and 11 AM. Total daily = 3.75 mg or 12 puffs.

**Table 5 - Reliever medication - Lpratropium or Ipratropium/short-acting  $\beta$  agonists [SABA] nebulizer solutions**

Total Daily Dose of Ipratropium (mg) in Ipratropium or Ipratropium/SABA Nebulizer Solutions	Number of Puffs*
0.5	4
1.0	8
1.5	12
2.0	16

\*Conversion factor: ipratropium or ipratropium/short-acting  $\beta$  agonists (SABA) nebulizer solution (with 0.5 mg Ipratropium) corresponds to 4 puffs

- Example of ipratropium or ipratropium/SABA nebulizer-to-puff conversion: Patient received 3 ipratropium or ipratropium/SABA nebulizer treatments (0.5 mg Ipratropium/treatment) between 7 and 11 AM. Total daily = 1.5 mg or 12 puffs.

## 6.2 PREPARATION/HANDLING/STORAGE/ACCOUNTABILITY

### Storage and handling

Investigators or other authorized persons (e.g., pharmacists) are responsible for storing the IMP/noninvestigational medicinal product (NIMP) in a secure and safe place in accordance with local regulations, labeling specifications, policies, and procedures.

Control of IMP storage conditions, especially control of temperature (eg, refrigerated storage) and information on in-use stability and instructions for handling the Sanofi compound must be managed according to the rules provided by the Sponsor in the pharmacy manual.

The expiry date is mentioned on the IMP labels (when required by country regulation), and storage conditions are written on the IMP labels.

1. The Investigator or designee must confirm appropriate temperature conditions have been maintained during transit for all study intervention and NIMP received and any discrepancies are reported and resolved before use of the study intervention.
2. Only participants enrolled in the study may receive study intervention and only authorized site staff may supply or administer study intervention. All study intervention and NIMP must be stored in a secure, environmentally controlled, and monitored (manual or

automated) area in accordance with the labeled storage conditions with access limited to the Investigator and authorized site staff.

3. The Investigator, institution, or the head of the medical institution (where applicable) is responsible for study intervention and NIMP accountability, reconciliation, and record maintenance (ie, receipt, reconciliation, and final disposition records).
4. Further guidance and information for the final disposition of used and unused study interventions are provided in a Pharmacy manual.

## **Preparation of IMP**

Dupilumab or matching placebo in glass pre-filled syringes will be dispensed to the patients.

## **Responsibilities**

The Investigator, the hospital pharmacist, or other personnel allowed to store and dispense the IMP/NIMP will be responsible for ensuring that the IMP/NIMP used in the clinical trial is securely maintained as specified by the Sponsor and in accordance with applicable regulatory requirements.

All IMP/NIMP will be dispensed in accordance with the Investigator's prescription and it is the Investigator's responsibility to ensure that an accurate record of IMP/NIMP issued and returned is maintained. For doses not given at study site, the home dosing diary will be used to record injections.

Any quality issue noticed with the receipt or use of an IMP/NIMP (deficiency in condition, appearance, pertaining documentation, labeling, expiration date, etc) must be promptly notified to the Sponsor. Some deficiencies may be recorded through a complaint procedure (see [Section 8.3.9](#)).

A potential defect in the quality of IMP/NIMP may be subject to initiation of a recall procedure by the Sponsor. In this case, the Investigator will be responsible for promptly addressing any request made by the Sponsor, in order to recall the IMP/NIMP and eliminate potential hazards.

Under no circumstances will the Investigator supply IMP/NIMP to a third party (except for DTP shipment, for which a courier company has been approved by the Sponsor), allow the IMP/NIMP/device to be used other than as directed by this clinical trial protocol, or dispose of IMP/NIMP/device in any other manner.

## **6.3 MEASURES TO MINIMIZE BIAS: RANDOMIZATION AND BLINDING**

### **6.3.1 Methods of assigning patients to treatment group**

A randomized treatment kit number list will be generated centrally by Sanofi for the IMPs. The IMPs (dupilumab or matching placebo) will be packaged in accordance with the list. The Sanofi Clinical Supply Chain team will provide the randomized treatment kit number list and the Study Biostatistician will provide the randomization scheme to the centralized treatment allocation system

(Interactive Voice Response System/Interactive Web Response System [IVRS/IWRS]). This centralized treatment allocation system will generate the patient randomization list according to which it will allocate the IMPs to the patients. The Investigator obtains treatment kit number at randomization and subsequent scheduled visits via an IVRS/IWRS that will be available 24 hours a day. Patients will be randomized in a 1:1 ratio to receive SC administrations of either:

- Dupilumab 300 mg q2w
- Matching placebo for dupilumab q2w.

Randomization will be stratified by country and by asthma history (yes or no).

Investigational medicinal products will be dispensed at the study visits summarized in SoA ([Section 1.3](#)).

Returned IMP from the patient's home should not be re-dispensed to the participants.

### **6.3.2 Methods of blinding**

Dupilumab and placebo will be provided in identically matched 2 mL pre-filled syringes. To protect the blind, each treatment kit of 2 mL (dupilumab / placebo) glass pre-filled syringes will be prepared such that the treatments (dupilumab and its matching placebo) are identical and indistinguishable and will be labeled with a treatment kit number.

In accordance with the double-blind design, study patients, Investigators, and study site personnel will remain blinded to study treatment and will not have access to the randomization arm or to the IMP content (dupilumab or placebo) except under circumstances described in [Section 6.3.3](#).

### **6.3.3 Randomization code breaking during the study**

In case of an AE, the code must only be broken in circumstances when knowledge of the IMP is required for treating the patient.

Code breaking can be performed at any time by using the proper module of the IVRS/IWRS and/or by calling any other phone number provided by the Sponsor for that purpose. If the blind is broken, the Investigator must document the date, time of day, and reason for code breaking.

Patient withdrawal will only occur when the code break call is made at the site level, not the study level. This means that if the Emergency Unblinding transaction is performed by the Investigator (ie, at the site level), then the patient will be withdrawn from treatment. However, if the Emergency Unblinding transaction is performed by the Global Safety Officer (GSO) (ie, at the study level, as the GSO is not site based), then the patient will not be withdrawn from treatment.

Patients who are withdrawn from treatment should be encouraged to remain in the study and the Investigator should discuss with them the key visits to attend (see [Section 7.2](#)).

## 6.4 STUDY INTERVENTION COMPLIANCE

The Investigator or pharmacist will also keep accurate records of the quantities of the IMP/NIMP received, dispensed, used, unused and returned/destroyed. The product accountability and inventory form/system is to be updated each time IMP/NIMP is dispensed. It must be established with the Investigator or other personnel designated by the Investigator and countersigned by the Investigator and the monitoring team. The study monitor will periodically check the supplies of the IMP held by the Investigator or pharmacist to verify accountability and inventory.

Treatment kit number has to be recorded on the appropriate page of the electronic Case Report Form (eCRF) and also on the product accountability and inventory form/system.

All used, partially used, or unused treatments will be destroyed at each respective site, after accountability and reconciliation have been performed. The site must not destroy the unused IMP/NIMP unless the Sponsor provides written authorization. Confirmation of destruction will be provided to the Sponsor.

## 6.5 CONCOMITANT THERAPY

Any medication or vaccine (including over-the-counter or prescription medicines, vitamins, and/or herbal supplements) that the participant is receiving at the time of enrollment or receives during the study must be recorded along with:

- Reason for use
- Dates of administration including start and end dates
- Dosage information including dose and frequency

The following concomitant medications are not permitted during the study from screening onwards:

- Use of any biologic agent within 5 half-lives of that compound before study entry (6 months if half-life is not known) and during the course of the study.
- Use of PDE4 inhibitors (roflumilast) and of theophylline during the course of the study unless stable > 6 months prior to screening visit.
- New chronic use of macrolide antibiotics (e.g. azithromycin) with the exception of AECOPD, in which case macrolides may be used up to 28 days.
- Systemic immunosuppressants (eg, methotrexate, any anti-TNF mAbs, B and/or T-cell targeted immunosuppressive therapies)
- Intravenous immunoglobulin (IVIG) therapy
- Live attenuated vaccines, refer to Appendix 7 ([Section 10.7](#))
- Beta-adrenergic receptor blockers (except for a selective beta-1 adrenergic receptor blocker used with dose stable 1 month prior to Visit 1)
- Other investigational drugs

**Note:** The following is a list of permitted concomitant medications during the study

- Maintenance treatment of COPD with ICS, LABA, LAMA, at a stable dosage, are allowed during the study
- Systemic corticosteroids in case of acute exacerbation up to a maximum of 6 weeks
- Rescue medication with SABA or short acting antimuscarinics (e.g. atrovent)

## **6.6 DOSE MODIFICATION**

Not applicable.

## **6.7 INTERVENTION AFTER THE END OF THE STUDY**

Not applicable.

## **7 DISCONTINUATION OF STUDY INTERVENTION AND PARTICIPANT DISCONTINUATION/WITHDRAWAL**

Withdrawal of consent for treatment (ie, treatment discontinuation at patient request) should be distinguished from (additional) withdrawal of consent for follow-up visits and from withdrawal of consent for non-patient contact follow-up (eg, medical record checks). The site should document any case of withdrawal of consent.

### **7.1 DISCONTINUATION OF STUDY INTERVENTION**

The IMP should be continued whenever possible.

In case the IMP is stopped, it should be determined whether the stop can be made temporarily; permanent IMP discontinuation should be a last resort. Any IMP discontinuation must be fully documented in the eCRF.

#### **7.1.1 Permanent discontinuation**

Permanent intervention discontinuation is any intervention discontinuation associated with the definitive decision from the Investigator not to re-expose the patient to the IMP at any time during the study, or from the patient not to be re-exposed to the IMP whatever the reason.

#### **List of criteria for permanent discontinuation of study intervention**

All efforts should be made to document the reason(s) for discontinuation of study intervention and this should be documented in the eCRF.

Patients must be withdrawn from the study for the following reasons:

- At their own request or at the request of their legally authorized representative (legally authorized representative means an individual or judicial or other body authorized under applicable law to consent on behalf of a prospective patient to the patient's participation in the procedure(s) involved in the research).
- If, in the Investigator's opinion, continuation in the study would be detrimental to the patient's well-being.
- At the specific request of the Sponsor.
- In the event of a protocol deviation, at the discretion of the Investigator or the Sponsor.
- Any code broken requested by the Investigator will lead to permanent discontinuation of study intervention.
- Pregnancy
- Anaphylactic reactions or systemic allergic reactions that are related to IMP and require treatment.

- Diagnosis of a malignancy during study, excluding carcinoma in situ of the cervix, or squamous or basal cell carcinoma of the skin.
- Any opportunistic infection, such as TB or other infections whose nature or course may suggest an immunocompromised status (see [Section 10.16](#), Appendix 16).
- Serum ALT >3 ULN and Total Bilirubin > 2ULN (see [Section 10.6](#), Appendix 6).
- Serum ALT > 5 ULN if baseline ALT ≤ 2 ULN or ALT >8 ULN if baseline ALT > 2 ULN (see [Section 10.6](#), Appendix 6).

Any abnormal laboratory value or ECG parameter will be immediately rechecked for confirmation before making a decision of permanent discontinuation of the IMP for the concerned patient.

See the SoA ([Section 1.3.2](#)) for data to be collected at the time of intervention discontinuation and follow-up and for any further evaluations that need to be completed.

### **Handling of participants after permanent study intervention discontinuation**

Patients who discontinue the study intervention prematurely (prior to completing the 52-week treatment period) will perform, as soon as possible, the ETD visit with all assessments normally planned for the EOT visit (Visit 16), to assure a complete clinical assessment in close temporal proximity to the premature termination of study treatment is available. In addition, to allow assessment of patient outcomes over the stipulated study period, patients will be asked and encouraged to complete all remaining study visits, and participate in all safety follow-up assessments according to the visit schedule with a ± 5 day window. For these patients the assessment schedule will be reduced (see [Section 1.3.2](#)) and visits during the planned treatment period may be conducted by phone (except for planned EOT) if patient is unable to come in for a site visit. Assessments not completed via phone should be performed at the next scheduled visit.

Patients will be followed-up according to the study procedures specified in this protocol up to the scheduled date of study completion (i.e. EOS, see [Section 1.3](#)), or up to recovery or stabilization of any AE to be followed-up as specified in this protocol, whichever comes last.

Patients who discontinue early from treatment may be asked to return to the clinic to have additional antidrug antibody (ADA) samples collected for analysis based on the overall assessment of antibody titers and/or clinical presentation at the time of discontinuation.

All cases of permanent discontinuation of study intervention should be recorded by the Investigator in the appropriate pages of the eCRF when considered as confirmed.

#### Temporary discontinuation of study intervention

Temporary discontinuation of study intervention may be considered by the Investigator because of AEs. Reinitiation of treatment with the IMP will be done under close and appropriate clinical/and or laboratory monitoring once the Investigator will have considered according to his/her best medical judgment that AE is sufficiently resolved and unlikely to recur after resuming therapy with IMP.

In addition, the following conditions(s) will be causes for temporary discontinuation of study intervention:

- Infections or infestations that do not respond to medical treatment
- Any laboratory abnormality that meets temporary treatment discontinuation criteria as per Appendix 6 ([Section 10.6](#))

If a patient is unable to return to clinic for a given visit within the specified visit window, patient should follow-up with all visit follow-up procedures planned for the subsequent visit (excluding randomization and EOT).

If the patient misses more than 3 consecutive doses, the patient will be permanently discontinued from the study.

For all temporary discontinuations of study intervention, duration must be recorded by the Investigator in the eCRF. Following a temporary interruption or missed dose, the IMP treatment should be reinitiated at the next scheduled visit, maintaining the original dose.

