### 1.3 SCHEDULE OF ACTIVITIES (SOA)

The schedule of activities (SoA) for patients who complete the planned treatment is described in [Section 1.3.1](#). Patients who withdraw from treatment prematurely must complete the ETD visit and follow the assessment in [Section 1.3.2](#) for the remaining visits.

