## 7.2 PARTICIPANT DISCONTINUATION/WITHDRAWAL FROM THE STUDY

A participant may withdraw from the study at any time at his/her own request, or may be withdrawn at any time at the discretion of the Investigator for safety, behavioral, compliance, or administrative reasons.

- If the participant withdraws consent for disclosure of future information, the Sponsor may retain and continue to use any data collected before such a withdrawal of consent.
- If a participant withdraws from the study, he/she may request destruction of any samples taken and not tested, and the Investigator must document this in the site study records.
- See SoA ([Section 1.3.2](#)) for data to be collected at the time of study discontinuation and follow-up and for any further evaluations that need to be completed.

Patients who withdraw from study treatment (prior to completing the planned duration of IMP treatment) will perform the ETD visit and will be asked and encouraged to complete all remaining study visits. Patients who withdraw from the study during the post-treatment phase should be encouraged to return for the EOS visit (for details see [Section 1.3.2](#) and [Section 7.1.1](#)). The value of all their study data collected during their continued involvement will be emphasized as important to the public health value of the study.

All study withdrawals should be recorded by the Investigator in the appropriate screens of the e-CRF, IVRS/IWRS and in the patient's medical records. In the medical record, at least the date of the withdrawal and the reason should be documented.

In addition, a patient may withdraw his/her consent to participate in the study. Withdrawal of consent for intervention should be distinguished from withdrawal of consent for follow-up visits and from withdrawal of consent for non-patient contact follow-up, eg, medical record checks. The site should document any case of withdrawal of consent.

Participants who have withdrawn from the study cannot be rerandomized (treated) in the study. Their inclusion and intervention numbers must not be reused.

If possible, the patients are assessed using the procedure normally planned for the end-of-study visit including a systemic drug concentration sample, if appropriate, and the Post treatment Period Visits.

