### 9.4.1 Efficacy analyses

**Table 9 - Efficacy analyses**

Endpoint	Statistical Analysis Methods

Primary
 
Annualized rate of moderate and severe COPD exacerbations over 52 week treatment period
	
The annualized rate of moderate and severe COPD exacerbation events will be analyzed using a negative binomial regression model. The model will include the total number of events occurring during the 52-week treatment period as the response variable, with the treatment group, region (pooled country), asthma history (Yes or No), smoking status at screening (current smokers or not), baseline disease severity (as % predicted post-bronchodilator FEV1), and number of moderate or severe COPD exacerbation events within one year prior to the study (<math>\leq 2</math>, 3, or <math>\geq 4</math>) as covariates. Log-transformed observation duration will be used as offset variable. The estimated annualized event rate for each treatment group and its two-sided 95% confidence intervals will be derived. The event rate ratio of the dupilumab group against placebo, its two-sided 95% confidence interval and p-value will be provided. Patients who permanently discontinue the study treatment will be encouraged to complete the study as planned and the additional off-treatment exacerbation events up to Week 52 will be included in the primary analysis. Sensitivity analyses for handling missing data may include pattern mixture model by multiple imputation and tipping point analyses.

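### Protocol Section 7.1.1 takes patients out of the study, not just off study drug, after more than three consecutive missed doses, which conflicts with the follow-up rules and the primary analysis

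*Protocol*

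**What the plan says.** Two sentences in protocol Section 7.1.1 send patients out of the study:

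- Under *Temporary discontinuation of study intervention*: "If the patient misses more than 3 consecutive doses, the patient will be permanently discontinued from the study".
- Under *List of criteria for permanent discontinuation of study intervention*: "Patients must be withdrawn from the study for the following reasons".

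The surrounding text treats the same situation as stopping drug while staying in follow-up:

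- Section 7.1.1 defines permanent discontinuation through a "definitive decision from the Investigator not to re-expose the patient to the IMP at any time during the study", or the equivalent decision by the patient.
- The paragraph on handling after permanent discontinuation, which sits between the two sentences, says: "Patients will be followed-up according to the study procedures specified in this protocol up to the scheduled date of study completion".
- Section 7.2 says that patients who stop study treatment "will perform the ETD visit and will be asked and encouraged to complete all remaining study visits".
- Section 1.3 says: "Patients who withdraw from treatment prematurely must complete the ETD visit and follow the assessment in" Section 1.3.2, which is the reduced schedule written for them.
- Section 6.3.3, on code breaks, says: "Patients who are withdrawn from treatment should be encouraged to remain in the study".
- The synopsis and Section 4.1 carry the same rule.

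Table 9 of the protocol relies on that follow-up: "the additional off-treatment exacerbation events up to Week 52 will be included in the primary analysis". SAP Sections 2.1.3.1 and 2.4.4.1 do the same. SAP 2.4.4.1 also ends observation at last contact for a patient who leaves the study early, and imputes nothing after that in the primary analysis.

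**The concern.** The protocol itself separates stopping treatment from leaving the study (opening of Section 7, and Section 7.2). The missed-dose sentence is automatic and uses the wrong one of the two terms. It has no qualifier limiting it to study drug and no cross-reference to the follow-up rules. A site that follows it to the letter is complying with the protocol while ending data collection that the primary estimand counts.

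Patients who reach four missed doses may include those whose drug was held for adverse events, unresponsive infections or laboratory abnormalities, so their later course is informative. Three things are at stake:

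- **Primary endpoint.** Off-drug exacerbation time up to Week 52 is lost. If the effect wanes off drug, losing it favours dupilumab.
- **SGRQ responders.** A patient with no Week 52 score is counted as a non-responder (SAP 2.4.4.2.3).
- **Safety.** Part of the 98-day treatment-emergent window (protocol 9.4.2) could go unobserved.

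Week 12 FEV1 is barely touched, because the rule acts before Week 12 only if the last dose was at Week 2 or earlier.

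**Working it through.** **Inputs from the documents.** Dosing is every 2 weeks with the last dose at Week 50 (protocol 1.3.1). Protocol 9.2 gives 924 patients (462 per arm), a placebo rate of 1.5 and a dupilumab rate of 1.125 per year (ratio 0.75), dispersion 1, 0.95 year mean duration and two-sided alpha 0.049.

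**The plan's own figure.** Wald test on the log rate ratio:

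- Variance = [(1/(0.95 × 1.5) + 1) + (1/(0.95 × 1.125) + 1)]/462 = 3.637/462 = 0.00787, so SE = 0.0887.
- |ln 0.75|/SE = 0.2877/0.0887 = 3.24. Subtracting 1.97 gives 1.27, hence power 89.9%.

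The stated 90% reproduces. This only confirms the rates used below.

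**When the rule bites.** With the last dose at Week t, doses are missed at t+2, t+4, t+6 and t+8. The fourth miss comes about 56 days after the last dose.

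- Follow-up lost to Week 52 = 52 − (t+8) = 44 − t weeks: 44 weeks for t = 0, 18 for t = 26, 2 for t = 42.
- Treatment-emergent window remaining = 98 − 56 = 42 days.

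**Assumptions.** The documents give no rate of four consecutive missed doses. I take t = 26 and a share f of patients removed, with f = 1% and 5% shown. The placebo rate is the same on or off study drug, so only the dupilumab arm moves. The ratios are total expected events over total time, an approximation to the regression estimate.

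**Patient-years lost.** 924 × f × 18/52 = 3.2 at 1% and 16.0 at 5%.

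**Case A: immediate return to the placebo rate from Week 28.** There are 24 off-drug weeks, of which 6 are observed if the patient is removed at Week 34.

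- Followed to Week 52: [(52 − 24f) × 1.125 + 24f × 1.5]/(52 × 1.5)
- Removed: [(52 − 24f) × 1.125 + 6f × 1.5]/[(52 − 18f) × 1.5]

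**Case B: effect lasts 98 days after the last dose.** The patient is then at the placebo rate for 12 weeks, none of them observed if removed. The 98 days is the plan's safety window, borrowed here as an assumption.

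- Followed to Week 52: 0.75 + 0.25 × f × 12/52
- Removed: 0.75

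| Case | f | Followed | Removed | Shift |
|---|---|---|---|---|
| A | 1% | 0.7512 | 0.7503 | 0.0009 |
| A | 5% | 0.7558 | 0.7515 | 0.0043 |
| B | 1% | 0.7506 | 0.7500 | 0.0006 |
| B | 5% | 0.7529 | 0.7500 | 0.0029 |

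If the effect persisted in full to Week 52, the shift would be zero.

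**The case against.** The best defence is that this is loose wording which context already corrects. The missed-dose sentence stands under a heading about study intervention, follows a definition framed as not giving the drug again, and comes just after the paragraph that requires follow-up. The stopping-criteria lead-in is corrected more clearly still, by its own heading, its code-break bullet and its closing pointer to Section 1.3.2. That stands as evidence of intent.

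There are also safeguards. Section 7.2, which governs leaving the study, sends even study-discontinued patients to Section 1.3.2, and asks for an end-of-study assessment and the post-treatment visits if possible. Section 8.3.4 follows SAEs and non-serious events of special interest to resolution or stabilization. The SAP plans multiple imputation, control-based imputation and a tipping-point analysis for missing exacerbations, and the sample size allows for 5% missing time. So the lost weeks and the 42 unobserved days are worst cases. The safeguards do not remove the point: the Section 7.2 request is conditional, and imputation tests the effect of missing data without recovering them. Section 7.2 also allows withdrawal for compliance reasons, but at the investigator's discretion, not automatically.

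Two stronger readings are tempting and unsupported:

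- **A larger bias.** A reader might infer that everyone who stops drug leaves the study at once. With 10% to 20% stopping mid-year and an immediate return to the placebo rate, the shift would be 0.25 × 0.5 × f = 0.0125 to 0.025. That relies on the lead-in which its context largely corrects, includes patients who leave at their own request and whom no rewording would keep, and assumes a stopping rate that no document gives.
- **A change in power.** A reader might infer that removal raises or lowers power. The direction depends on whether the effect lasts off drug, which the documents do not say.

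**Conclusion.** The contradiction is real within the supplied protocol. An automatic rule, read as written, ends follow-up that the neighbouring paragraph requires and that the primary analysis counts. A reader might go further and infer that the trial was designed to drop off-drug patients. The definition, the reduced schedule and Table 9 all say otherwise, so this is wrong wording in an operative rule and not a chosen design.

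The numerical effect is unknown and probably small: about 16 patient-years and a rate-ratio shift of about 0.003 to 0.004 in dupilumab's favour. That rests on an assumed 5% of patients removed, an assumed last dose at Week 26, and an effect that wanes off drug. The wording should be corrected because lost follow-up cannot be recovered and the correction costs almost nothing, not because the primary result is in danger.

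One limit applies. SAP Section 1.5 refers to protocol amendment 7, and the SAP differs from the supplied protocol on primary endpoints and randomization strata. Whether these sentences survive in amendment 7 cannot be checked. The no-imputation rule comes from the SAP alone.

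**What to change.** In protocol Section 7.1.1:

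1. **Missed-dose sentence.** Say that the patient is *permanently discontinued from study intervention*, and point to the paragraph on handling after permanent discontinuation and to Section 1.3.2.
2. **Lead-in to the stopping criteria.** Replace it with *Study intervention must be permanently discontinued for the following reasons*.
3. **Second bullet of that list.** Change *continuation in the study* to *continuation of study intervention*, so that it matches the new lead-in.

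Leave genuine withdrawal from the study to Section 7.2.

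The cost is close to nil: three small wording changes, one cross-reference and a clarification letter to sites. The reduced follow-up schedule already exists, and the sample size and analysis do not change.
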